6.2. Hyperpigmentation Assessment

Summaries (number and percentage of subjects) of hyperpigmentation (overall and by body location) will be provided using the safety analysis set. Multiple occurrences will be counted once only per subject in each summary. Hyperpigmentation assessment data will also be listed.

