1.1. Study Objectives

The objectives of this study are:

- To provide current FTC-203 study participants in South Africa with continued access to the study drug, emtricitabine, following completion of the FTC-203 study.
- To collect long-term safety information in subjects receiving emtricitabine in combination with other antiretroviral agents.

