1.2. Study Design

1.2.1. Design Configuration

This is an open-label, non-randomized rollover protocol that will provide current FTC-203 study participants enrolled at the two study centers in South Africa with continued access to the study drug, emtricitabine, following completion of the FTC-203 study. A total of 59 subjects were enrolled in South Africa at two study centers, representing the maximum possible enrollment in this protocol.

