1.2.2. Subject Population

HIV-1 infected pediatric subjects enrolled in FTC-203 at two study centers in South Africa who wish to continue to receive the study drug, emtricitabine, beyond completion of the FTC-203 study were eligible for enrollment. Subjects must have completed at least 96 weeks on the FTC-203 study and were required to complete the End-of-Study Visit for FTC-203 prior to transitioning into the rollover protocol.

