1.2.5. Study Periods/Phases and Duration

Each eligible subject electing to participate in the rollover protocol continued to receive emtricitabine, in combination with other antiretroviral medications, for as long as they continued to meet the following virologic criteria:

- they have a plasma HIV-1 RNA viral load of ≤ 400 copies/mL, or
- if the subject's plasma HIV-1 RNA viral load is > 400 copies/mL, their viral load is $< 1.0 \log_{10}$ above the nadir recorded after Week 8 of the FTC-203 study and there is reliable genotypic evidence showing a lack of resistance to emtricitabine,

and until either: (1) the subject chooses to discontinue treatment of emtricitabine and withdraw from the rollover protocol; (2) the subject experiences a toxicity that necessitates the permanent discontinuation of emtricitabine, or (3) emtricitabine is approved for market distribution in the subject's country of residence.

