2.4. Analysis Windows

Study Day 1 is defined as the day when the first dose of study drug in this study, as recorded on the study drug accountability case report form. Baseline visit is defined as the Study Day 1 visit.

Study Day is calculated relative to Study Day 1. For events that occurred on or after Study Day 1, Study Day is calculated as (visit date minus date of the first dose plus 1). For events that occurred prior to Study Day 1, Study Day is calculated as (visit date minus date of the first dose).

Subject visits might not occur on protocol-specified days. Therefore, for the purpose of analysis, observations will be assigned to analysis windows.

The analysis windows (for height, weight, AE visits, etc) are presented in Table 2-1.

Table 2-1. Analysis Windows

	Nominal Day	Visit Window
Baseline		≤ 1
Week 12	84	[2, 126]
Week $12*k$, $k = 2, 3, \dots, 43$	$84*k$	[$84*k-41, 84*k+42$]

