3.2. Disposition of Subjects

The summary of subject disposition will be provided. This summary will include the number of subjects enrolled and subjects in the safety analysis set.

In addition, the number and percentage of the subjects in the following categories will be summarized:

- Subjects completing study. These are subjects whose reasons for discontinuation are end of study, or end of rollover study;
- Subjects rolled over to Study GS-US-292-1515;
- Prematurely discontinued study (with summary of reasons for discontinuing study).

The denominator for the percentages of subjects in the above category will be the number of subjects in the safety analysis set.

A data listing of reasons for study drug discontinuation will be provided.

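### The SAP reports hyperpigmentation only as a number and percentage of treated subjects and summarises no exposure, so the table says little about long-term safety

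*SAP*

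**What the plan says.** - **Objective.** SAP 1.1 gives two aims. One is continued access to drug; the other is "To collect long-term safety information in subjects receiving emtricitabine in combination with other antiretroviral agents".
- **Summary.** SAP 6.2: "Summaries (number and percentage of subjects) of hyperpigmentation (overall and by body location) will be provided using the safety analysis set". A subject counts once per summary however many occurrences there are, and the assessment data are also listed. The denominator (SAP 2.2) is every enrolled subject with at least one dose.
- **Treatment length.** SAP 1.2.5 has subjects continue emtricitabine "for as long as they continued to meet the following virologic criteria", ending earlier on withdrawal, toxicity or local market approval. No calendar end is given.
- **Windows.** SAP 2.4: "The analysis windows (for height, weight, AE visits, etc) are presented in Table 2-1". The table runs to k = 43 intervals of 12 weeks. The planned summaries are disposition (3.2), demographics (4) and hyperpigmentation (6.2), and none is by window.
- **Exposure.** Accountability data are listed (SAP 3.3), as are reasons for stopping study drug (SAP 3.2). Neither document summarises duration of treatment or person-years. The first-dose date is available, because Study Day 1 is taken "as recorded on the study drug accountability case report form".
- **Prior treatment time.** SAP 1.2.2: "Subjects must have completed at least 96 weeks on the FTC-203 study".
- **Onset dates.** Protocol 7.2 has the date of onset recorded for serious events, events leading to permanent discontinuation and hyperpigmentation. SAP 6.1 says that event details such as the start date were collected only for events leading to study termination. Protocol 7.7.1 adds a dedicated hyperpigmentation form, whose fields are not shown.

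**The concern.** Under these rules a subject treated for one 12-week interval and a subject treated for many years carry equal weight in the denominator. The resulting percentage is the share of subjects ever recorded over follow-up that differs between subjects and is not reported. It is neither a rate nor a risk at a stated time.

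This matters because hyperpigmentation is the only adverse event type given its own summary table; serious events and events leading to termination are only listed (SAP 6.1). It is therefore the main tabulated result bearing on the long-term safety objective, and it will be read without knowing whether the cases arose over, say, 100 or 500 person-years. Listings would let a determined reader rebuild exposure, but each reader would have to choose an end date and a treatment of interruptions.

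**Working it through.** The plan states no event count, rate or exposure, so there is no figure of its own to reproduce. The check has four steps.

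**1. How long the SAP provides for.** From SAP Table 2-1, the last window closes on Day 84 × 43 + 42 = 3654, and 3654/365.25 = 10.0 years. This is what the windows allow, not evidence of how long anyone was followed. Time on FTC-203 before entry is at least 96 × 7/365.25 = 1.84 years.

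**2. What one percentage can stand for.** The only documented input is the maximum enrolment: "A total of 59 subjects were enrolled in South Africa at two study centers" (SAP 1.2.1). The 6 cases and the mean exposures are assumptions. The crude result is 6/59 = 10.2% (exact 95% CI 3.8 to 20.8%). Person-years are PY = 59 × mean years, the rate is 6/PY, and the exact Poisson limits are χ²(0.025; 12)/(2PY) and χ²(0.975; 14)/(2PY).

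| Assumed mean exposure (years) | PY | Crude % | Per 100 PY (95% CI) |
|---|---|---|---|
| 1 | 59 | 10.2 | 10.2 (3.7 to 22.1) |
| 2 | 118 | 10.2 | 5.1 (1.9 to 11.1) |
| 5 | 295 | 10.2 | 2.0 (0.7 to 4.4) |
| 8 | 472 | 10.2 | 1.3 (0.5 to 2.8) |

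The rows are alternative studies. The spread between them comes from the chosen exposures by construction and is not uncertainty in this study's result.

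Conversely, at an assumed constant rate of 5 per 100 PY the expected crude proportion 1 − exp(−0.05t) is 4.9% at 1 year, 22.1% at 5 years and 39.0% at 9.9 years.

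**3. How much the end-of-exposure rule matters.** Suppose the rule adds one full 12-week interval per subject: 59 × 84/365.25 = 13.57 PY.

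| Assumed mean exposure (years) | Rate before | Rate after | Change |
|---|---|---|---|
| 1 | 10.2 | 6/72.57 = 8.3 | −19% |
| 2 | 5.1 | 6/131.57 = 4.6 | −10% |
| 5 | 2.0 | 6/308.57 = 1.9 | −4% |
| 8 | 1.3 | 6/485.57 = 1.2 | −3% |

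The rule matters if follow-up is short, so it has to be written down. The effect of interruptions cannot be tested from the documents.

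**4. Total exposure against time to first onset.** At 8 years and 472 PY, total exposure gives 6/472 = 1.27 per 100 PY. If all six onsets fell on Day 1, time at risk would give 6/(472 − 48) = 1.42 if the cases had average follow-up, or 6/(472 − 60) = 1.46 if each case had 10 years. The gap depends on how long the cases themselves were followed, which is not known.

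**The case against.** The strongest reply is that nothing here is wrong. SAP 6.2 calls its result a number and percentage and never a rate. Protocol Section 8 plans no statistical analyses for what is a single-arm access study of at most 59 subjects, with no endpoint or comparator. Accountability, discontinuation and hyperpigmentation data are all listed. A plain exposure table would answer the question of how much treatment time was observed, and a rate with an interval goes further than the plan intended. The rate would also not be a rate from first dose, because subjects arrive after at least 96 weeks on FTC-203.

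Much of this stands. The percentage is correct for what it counts, the confidence interval is optional, and the clock's starting point must be footnoted. It does not remove the gap. Section 8 also foresees tabular summaries, and an exposure table is as descriptive as the demographic table already planned. Listings leave the conventions to each reader.

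A reader might go further and infer any of the following, which the documents do not support:

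- **The percentage is biased, in a known direction.** No follow-up distribution is given, so no direction can be claimed.
- **Subjects were in fact followed for ten years.** The windows only allow for it.
- **The data already collected are certainly sufficient.** Protocol 5.2.3 puts dispensing and return dates in a site log or equivalent. Protocol 6.2.2 sends dispensing and accountability information to the CRF without saying which dates.

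**Conclusion.** The point holds as a reporting gap and a cheap improvement, not as an error in the percentage. Treatment length is open-ended, the only planned hyperpigmentation summary is a crude number and percentage, and no exposure summary exists in either document, although long-term safety is a stated objective. Reporting exposure and a rate per person-year would change what that table can be used to conclude.

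The practical size is unknown. It depends on the number of cases and the spread of follow-up, neither of which the documents give; every rate shown above rests on assumed values for both. If all subjects turn out to have similar, long exposure, the added table will simply say so.

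Whether time to first onset can be used is open. Protocol 7.2 and SAP 6.1 cannot both describe the data collected on hyperpigmentation onset, unless the dedicated form carries the date.

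**What to change.** Keep the number and percentage, and add to the SAP:

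1. A descriptive table of emtricitabine exposure from Study Day 1: total person-years, median, Q1, Q3, minimum and maximum, derived from accountability and discontinuation data. State the end-of-exposure convention and how treatment interruptions (permitted by Protocol 6.4 and 7.6) are counted.
2. Beside the hyperpigmentation percentage, the number of subjects with hyperpigmentation per 100 person-years of total exposure, optionally with an exact Poisson 95% CI. Footnote that the clock starts at rollover entry, after at least 96 weeks on FTC-203, so this is not a rate from first emtricitabine dose.
3. A statement reconciling Protocol 7.2 with SAP 6.1 on onset dates. Use time to first onset only if the Hyperpigmentation Assessment CRF carries them; otherwise use total exposure and say so.

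The cost is one table, one extra row and one written convention. Whether existing CRF data are enough depends on which accountability dates were entered; the first-dose date is there, but return or last-dose dates are not confirmed. There are two drawbacks. The end of exposure may be known only to within a dispensing interval, which can move the rate materially when follow-up is short. And a single average rate hides any change over time.

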6.3. Baseline Antiretroviral (ARV) Regimen

Baseline ARV regimen for this study will be listed.

Appendix 1. Study Procedures Table

Assessment	FTC-203	GS-US-162-0112 ¹		
	End-of-Study ²	Baseline Visit ³	+ each 12 weeks ⁴	Subject Discontinuation
Informed Consent		x		
Review of Incl./Excl. Criteria		x		
Physical Examination	x			
Height/Weight/Vital Signs	x	x ⁵	x ⁵	x ⁵
Hematology	x			
Chemistry	x			
Urinalysis	x			
Pregnancy Test ⁶	x			
CD4+ Cell Count	x			
Plasma HIV-1 RNA Levels	x	x	x	x
Plasma for Storage (5 mL)	x			
Record Adverse Events	x	x ⁷	x ⁷	x ⁷
Record HIV-1 Related Events	x			
Study Drug Accountability	x	x	x	x
Dispense Study Drug ⁸		x	x	
Concomitant Medications	x			

1. Only for qualifying subjects, i.e., subjects who meet the virologic criteria for continuation of emtricitabine at the End-of-Study Visit for FTC-203 (see Section 6.2.2 of the protocol).
2. These assessments will be performed on all subjects who discontinue the FTC-203 study, regardless of reason, including those subjects who complete the FTC-203 study and who elect not to participate in the rollover protocol.
3. If there is a reasonable expectation that the subject will continue to meet the virologic criteria for continuation of emtricitabine, based on the results of HIV-1 RNA viral load testing performed during the FTC-203 study, then the End-of-Study Visit for FTC-203 and the Baseline Visit of the GS-US-162-0112 rollover protocol may be completed at the same clinic visit.
4. The Investigator may choose to have the subject return to the clinic on a more frequent basis, e.g., as part of their standard of care, and/or to resupply the study drug(s) (and other medications) but these visits will be outside of the protocol-defined visit schedule.
5. Height (or length) and body weight only, if the subject has not maintained the same height for three consecutive protocol visits (36 weeks), or if the height and weight are necessary to determine study drug dosage.
6. If the pregnancy test is positive, discontinue emtricitabine and contact Gilead Sciences. A positive urine β -HCG test should be confirmed with a serum β -HCG test, per the FTC-203 protocol.
7. Adverse events will only be recorded in the CRF if the event (s) is (1) serious, (2) results in the permanent discontinuation of study drug, emtricitabine, and/or (3) is associated with skin discoloration (hyperpigmentation).
8. Subjects will receive emtricitabine, in combination with other antiretroviral medications, at 6 mg/kg once daily (QD), up to a maximum of 200 mg QD using the capsule formulation or up to 240 mg QD using the oral solution formulation, each administered orally, for as long as the subject continues to demonstrate virologic success. Although assessments are scheduled at 12-week intervals, no more than a 60-day supply of emtricitabine oral solution may be dispensed to subjects who do not have means to adequately refrigerate the drug at home, thereby necessitating more frequent visits by the subject to the clinic to resupply the study drug. Drug accountability information will be recorded at those visits.
